Appendix A Local administration site TEAEs:

High-Level Group Terms (HLGTs)

- Oral soft tissue conditions
- Salivary gland conditions
- Tongue conditions

High-Level Terms (HLTs)

- Gingival disorders, signs, and symptoms NEC
- Gingival haemorrhages
- Dental and oral soft tissue infections

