The SQ tree SLIT-tablet was generally well-tolerated with a safety profile characterised by frequent but transient local allergic events in the first few days of treatment, primarily occurring in or around the mouth and throat (e.g. pruritus, irritation, sensation changes, discomfort, swellings, and pain), that were typically assessed as mild or moderate in intensity. Severe allergic reactions were uncommon. Overall, the SQ tree SLIT-tablet was well-tolerated in subjects with tree pollen allergy with no major safety concerns detected. Finally, the safety profile was generally similar across age subgroups (adolescent vs adult).

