1.3 Trial rationale

The prevalence of allergy induced by birch and cross-reactive tree pollen in children and adolescents in the general population is 14-16% (Schmitz et al. 2013; Stemeseder et al. 2017). A substantial number of these children and adolescents do not reach sufficient symptom control when treated with pharmacotherapy (antihistamines/steroids) (Meltzer et al. 2009). Furthermore, most subjects with birch pollen allergy are poly-sensitised to pollen from related trees and may experience symptoms to early and/or late flowering trees in the birch homologous group. Thus, the symptom burden extends beyond the birch season and therefore this trial will evaluate symptoms and medication use during the birch pollen season and also during the alder/hazel, and oak pollen seasons.

The SQ tree SLIT-tablet has been demonstrated in adults with AR/C induced by pollen from the birch group to be efficacious in reducing the symptoms of AR/C, and has an acceptable safety and tolerability profile with few reported serious AEs (SAEs), of which none were assessed as related to the SQ tree SLIT-tablet (12 SQ-Bet). Furthermore, the TT-04 trial did not provide evidence that the efficacy and safety profile of the SQ tree SLIT-tablet differs between adults and adolescents. The SQ tree SLIT-tablet has yet to be studied in children <12 years old.

Clinical trial protocol	Date:	24-May-2020	
Trial ID: TT-06	Version:	3.0	
EudraCT No: 2020-004372-17	Status:	Final	
CONFIDENTIAL	Page:	26 of 99	

Currently, there is no approved SLIT product in Europe or North America for the treatment of allergy in children with a history of AR/C symptoms induced by pollen from the birch group and treatment in adolescents is only authorised in Switzerland.

Therefore, there is an unmet clinical need to develop a treatment that can expand the treatment options for children and adolescents suffering from AR/C induced by pollen from the birch group.

This trial is a part of the phase III development programme for the SQ tree SLIT-tablet. The purpose of this trial is to evaluate the efficacy and safety of the SQ tree SLIT-tablet in paediatric subjects (5 through 17 years of age) with persistent moderate to severe AR/C (with or without asthma) induced by pollen from the birch group despite being treated with symptom-relieving medication.

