1.4 Benefit-risk assessments

The SQ tree SLIT-tablet provides an alternative formulation and mode of administration of immunotherapy that expands the treatment options for children suffering from AR/C induced by pollens from the birch group. The orodispersible dosage form is ideally suited for the treatment of children as it is easy to administer, and the rapid dispersion makes it difficult to spit out or aspirate (EMEA 2006).

The SQ tree SLIT-tablet is an effective treatment for adult patients for whom AIT is indicated and has an acceptable safety profile in this population. In contrast to SCIT treatments, the SQ tree SLIT-tablet does not require up- or down-titration and allows for at-home dosing after administration of the first dose in a health care setting under the supervision of a physician with experience in the treatment of allergic diseases.

In the current trial, the SQ tree SLIT-tablet may show an effect on symptom relief and reduce the use of symptom-relieving medication in children as well. Thus, subjects on active treatment in the trial may receive a direct benefit of access to a new treatment that is not yet commercially available.

All subjects participating in the trial will have access to symptom-relieving medication and will receive expert medical care. Their participation will contribute to the development of the new treatment for children suffering from allergy induced by pollen from the birch group.

The SQ tree SLIT-tablet has been demonstrated to be well-tolerated and suitable for self-administration in adults. Typical adverse reactions are transient local reactions occurring within the first few days of treatment. These are expected in paediatric subjects as well. Other potential adverse reactions are class effects of AIT/SLIT and include acute worsening of asthma symptoms (exacerbation), EoE, anaphylactic reactions, and serious laryngo-pharyngeal reactions. However, these reactions are rare and are not expected to increase in the paediatric population.

Risks in this trial are manageable when the first SLIT-tablet is administered under physician supervision and with appropriate education of the subject and parent/guardian about symptoms and signs of severe allergic reactions. There is no expectation of an increased safety risk for children enrolled in this trial compared with that observed in adults in previous tree pollen trials.

Clinical trial protocol	Date:	24-May-2020	
Trial ID: TT-06	Version:	3.0	

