6.9.2.1 Events of special interest

Events of special interest for this trial are:

- Systemic allergic reactions including anaphylaxis
- Events treated with adrenaline/epinephrine
- Severe local swelling or oedema of the mouth and/or throat
- Oral allergy syndrome
- Eosinophilic oesophagitis
- Asthma exacerbations

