6.9.2.3 Local administration site TEAEs

The AEs identified as local administration site TEAEs, by comparison against a pre-defined list of MedDRA PTs, will be summarised separately. The pre-defined list of PTs is given in section Appendix A.

IMP-related local administration site reactions TEAEs will be summarised similar to all TEAEs by treatment group according to causality, severity (mild, moderate, severe), seriousness, action taken, outcome, and whether the event led to IMP discontinuation.

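### The list that defines local administration site TEAEs names only oral structures, gives no preferred terms and does not say whether throat reactions count

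*SAP*

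**What the plan says.** Local reactions to the tablet are a named safety endpoint. Protocol 2.11 and SAP 3.1 (Table 1) both define it by a pre-specified set of MedDRA preferred terms. Protocol 15.13.1 repeats that approach and leaves further detail to the SAP.

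SAP 6.9.2.3 then says: "The pre-defined list of PTs is given in section Appendix A". Events that match are summarised separately. The IMP-related ones are broken down by treatment group "according to causality, severity (mild, moderate, severe), seriousness, action taken, outcome, and whether the event led to IMP discontinuation".

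Appendix A contains three High-Level Group Terms and three High-Level Terms. The first is "Oral soft tissue conditions". The others cover the salivary glands, the tongue, the gums (two entries) and infections of the teeth and oral soft tissue.

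Elsewhere the documents place local events more widely. Protocol 1.2 describes the local allergic events of earlier trials as "primarily occurring in or around the mouth and throat (e.g. pruritus, irritation, sensation changes, discomfort, swellings, and pain". The events of special interest in SAP 6.9.2.1 include "Severe local swelling or oedema of the mouth and/or throat".

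**The concern.** There are two separate difficulties.

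- **Form.** Four places promise preferred terms, and the appendix they depend on lists none. A reader cannot see from the SAP which terms will be counted.
- **Scope.** Both documents speak of local events in the mouth and the throat, but the list that defines the endpoint names only the mouth. If the groupings contain no throat terms, a subject with a throat-only reaction falls outside the pooled count and its breakdown.

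Local reactions are the characteristic safety finding for this product. Of local reactions, protocol 1.4 says "These are expected in paediatric subjects as well". Protocol 1.3 adds that "The SQ tree SLIT-tablet has yet to be studied in children <12 years old". The pooled figure is therefore likely to be used as the summary of local tolerability in a new age group, and its scope should be explicit.

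**Working it through.** The plan gives no figure to reproduce. The check is a count and a comparison of texts.

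**1. What Appendix A lists**

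| Level | Structure named | Names throat or pharynx? |
|---|---|---|
| HLGT | Oral soft tissue | No |
| HLGT | Salivary glands | No |
| HLGT | Tongue | No |
| HLT | Gums (disorders, signs and symptoms) | No |
| HLT | Gums (bleeding) | No |
| HLT | Teeth and oral soft tissue (infections) | No |

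3 HLGTs + 3 HLTs = 6 groupings. Groupings naming the throat or pharynx: 0 of 6. Preferred terms listed: 0.

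**2. Where the documents place local events.** Protocol 1.2 says mouth and throat. In SAP 6.9.2.1, 1 of the 6 types of event of special interest names the throat, and it calls the event local. SAP 6.11, which records changes from the protocol, re-labels the endpoint as treatment-related local administration site TEAEs. It records neither an oral-only restriction nor a move from preferred terms to groupings.

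**3. What would happen to a mild throat-only reaction, taking the grouping names at face value**

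| Output | Would it appear? |
|---|---|
| Pooled local administration site summary (SAP 6.9.2.3) | Apparently not |
| All-TEAE table by SOC and PT (SAP 6.9.2.2) | Yes |
| IMP-related TEAE table by SOC and PT (SAP 6.9.2.2) | Yes, if judged related |
| Serious, interruption and discontinuation outputs (SAP 6.9.2.2) | Only if it qualifies |
| Severe local swelling event of special interest (SAP 6.9.2.1) | No, because it is not severe |

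The last row matters because protocol 1.2 reports local events "that were typically assessed as mild or moderate in intensity".

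**4. Whether the other tables can replace the pooled figure.** They cannot. The SOC and PT tables count subjects within each term. One subject may have several events, so the rows cannot be added to give the number of subjects with any mouth or throat reaction. No output in the SAP gives that number.

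**5. Size.** The documents give no rate of throat-only reactions and no overlap between mouth and throat events, so no size can be derived. As an illustration only, take the planned 500 subjects in the active arm, assume that throat terms are not covered, and assume a throat-only rate *r*. The number of subjects outside the pooled count is 500 × *r*:

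- *r* = 1%: 500 × 0.01 = 5
- *r* = 5%: 500 × 0.05 = 25
- *r* = 10%: 500 × 0.10 = 50

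These rates are assumptions. Nothing in the documents supports one over another.

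**The case against.** **The omission is inferred from names.** What a grouping is called does not prove what it contains. The MedDRA 23.1 hierarchy fixed in SAP 6.9.2 would settle the matter, but it is not in the documents. This stands. A reader might infer that the plan under-counts local reactions, and the documents do not show that.

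**An oral scope fits the endpoint's wording.** The endpoint concerns the administration site, and protocol 9.1 has the tablet disperse under the tongue. Protocol 1.2 is background on earlier trials and defines no endpoint. Where the sponsor wanted the throat covered, as in the events of special interest, it said so. This stands as a possible reading, so one cannot say that the SAP contradicts the protocol's definition. It does not settle the point. The list already reaches beyond the area under the tongue to gums, salivary glands and dental infections, and no passage says whether the throat is in or out.

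**Throat events are reported elsewhere.** This is true. A reader might infer that they drop out of safety reporting, and that would be wrong. They stay in the TEAE tables. Frequent IMP-related terms also get onset and duration summaries, and severe throat swelling is an event of special interest. What is missing is one pooled count.

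**The summary is descriptive.** It is outside the testing hierarchy in SAP 4.1.1 and no decision rule depends on it. This stands, and it limits the weight of the point.

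**The groupings are reproducible.** With the MedDRA version fixed they resolve to a fixed set of terms, and SAP section 3 calls Appendix A simply a list of terms. This stands too. The mismatch in form is one of transparency, not of an undefined rule.

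**Conclusion.** The point holds as a worthwhile and inexpensive improvement to a descriptive safety summary. Two things are established from the text: Appendix A lists no preferred terms although four places promise them, and none of its six groupings names the throat although the documents describe local events there. It is probable but not established that following the list as written gives an oral-only pooled figure. That conclusion rests on the grouping names.

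If throat terms are indeed not covered, and the throat was meant to be in scope, the direction is an under-count of subjects with any local reaction. The amount is unknown. No efficacy result, hypothesis test or individual-term safety table is affected.

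**What to change.** Before unblinding:

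1. List in Appendix A the MedDRA 23.1 preferred terms to which the six groupings resolve. If throat terms are already among them, this will show it.
2. Keep the oral summary as planned.
3. Add one mouth-and-throat summary row that includes any throat or pharyngeal preferred terms not already covered.
4. State which of the two is the endpoint in SAP Table 1.

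The cost is an edit to one appendix, a coding look-up and one extra row. The downside is that the reported local-reaction rate may rise. Settling the scope while blinded prevents the choice from looking data-driven.

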Appendix B Further details to statistical analyses

Table 10: LME analyses

LME output	Adjusted means for each treatment group, the absolute treatment difference (Placebo – Active) with 95% confidence interval and p-value, and the relative treatment difference (Placebo – Active/ Placebo) with 95% confidence interval will be presented.
Without multiple imputation	
Endpoint	
The endpoint is analysed as the response variable in a LME model which includes relevant fixed and random effects, and with different residual errors specified for each treatment group. The model will be estimated using REML, and the Kenward and Roger's approximation (Kenward and Roger 1997) is used to calculate the denominator degrees of freedom.
 
The p-value for the absolute difference is reported as the test result. The 95% CI for the relative difference will be calculated using Fieller's theorem (Fieller 1954).

Square root transformed endpoint	
The square root transformed endpoint is analysed as the response variable in a LME model which includes relevant fixed and random effects, and with different residual errors specified for each treatment group. The model will be estimated using REML, and the Kenward and Roger's approximation (Kenward and Roger 1997) is used to calculate the denominator degrees of freedom.
 
The results are back-transformed as follows: estimated least square means of the square root transformed endpoint are output along with the associated covariance matrix. The absolute difference is calculated by squaring the adjusted means, and then calculating the difference. For the absolute difference the SE is approximated by using the first order Delta method (first order Taylor approximation), and from this the 95% CI is calculated. For the relative difference, Fieller's theorem (Fieller 1954) is used to calculate the 95% CI for X/Y, and then the 95% confidence bounds for $(Y^2 - X^2)/Y^2 = 1 - (X/Y)^2$ are found by applying the monotone transformation $f(r) = 1 - r^2$ to the confidence interval.

With multiple imputation	
Imputation will be done using the method of unrestricted random sampling with replacement (seed=7127) and 1000 multiple imputed datasets will be created.	
Endpoint	
Each of the 1000 multiple imputed datasets is analysed using the model specified for the endpoint. The endpoint is analysed as the response variable in a LME model which includes relevant fixed and random effects. The model will be estimated using REML, and the Kenward and Roger's approximation (Kenward and Roger 1997) is used to calculate the denominator degrees of freedom.
 
Rubin's rule is used to combine the 1000 analysis results across the multiple imputed datasets. The p-value for the absolute difference is reported as the test result. The 95% confidence interval for the relative difference is calculated using Fieller's theorem (Fieller 1954).

Square root transformed endpoint	
Each of the 1000 multiple imputed datasets is analysed using the model specified for square root transformed endpoint. The square root transformed endpoint is analysed as the response variable in a LME model which includes relevant fixed and random effects, and with different residual errors specified for each treatment group. The model will be estimated using REML, and the Kenward and Roger's approximation (Kenward and Roger 1997) is used to calculate the denominator degrees of freedom.
 
Rubin's rule is used to combine the 1000 analysis results across the multiple imputed datasets. The p-value for the absolute difference is reported as the test result.
 
The results are back-transformed as follows; after Rubin's rule is used to combine results across imputations, estimated least square means on the square root transformed scale are output along with the associated covariance matrix. The absolute difference is calculated by squaring the adjusted means, and then calculating the difference. For the absolute difference the SE is approximated by using the first order Delta method (first order Taylor approximation), and from this the 95% CI is calculated. For the relative difference, Fieller's theorem (Fieller 1954) is used to calculate the 95% CI for X/Y, and then the 95% confidence bounds for $(Y^2 - X^2)/Ys^2 = 1 - (X/Y)^2$ are found by applying the monotone transformation $f(r) = 1 - r^2$ to the confidence interval.

----------------------------------	--

Convergence issues:

If the model does not converge due, then the random effect pollen station will be pooled into larger groups. If the model still does not converge, the random effect of pollen within cohort will be removed from the model.

Model checking:

The assumption of normally distributed residuals underlying the LME model will be evaluated by visual inspection of quantile-quantile plots for the primary and key secondary endpoints

Square root transformation:

The LME relies on the assumption of normally distributed residuals. Therefore, the square root transformation is generally applied, as this usually results in a good approximation to the so-called normal distribution. In addition, the square root transformation is used as the DMS scores are skewed with a lot of 0's, which is the reason for not using a log transformation.

Mean and SE

Let $\mu_{placebo}$, μ_{Active} , $\sigma^2_{Placebo}$, and σ^2_{Active} be the resulting means and variances for placebo and active treatment and cov be the covariance. Then the back-transformed means are given by:

- $\hat{\mu}_{Placebo} = (\mu_{Placebo})^2$
- $\hat{\mu}_{Active} = (\mu_{Active})^2$
- $\hat{\mu}_{Difference} = (\mu_{Placebo})^2 - (\mu_{Active})^2$

and the back-transformed standard errors are given by

- $SE_{Active} = \sqrt{(2\mu_{Active})^2 \sigma_{Active}}$
- $SE_{Placebo} = \sqrt{(2\mu_{Placebo})^2 \sigma_{Placebo}}$
- $SE_{Difference} = \sqrt{(2\mu_{Placebo})^2 \sigma_{Placebo} + (-2\mu_{Active})^2 \sigma_{Active} + 2(2\mu_{Placebo})(-2\mu_{Active})cov}$

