The results are back-transformed as follows; after Rubin's rule is used to combine results across imputations, estimated least square means on the square root transformed scale are output along with the associated covariance matrix. The absolute difference is calculated by squaring the adjusted means, and then calculating the difference. For the absolute difference the SE is approximated by using the first order Delta method (first order Taylor approximation), and from this the 95% CI is calculated. For the relative difference, Fieller's theorem (Fieller 1954) is used to calculate the 95% CI. More details can be found in Appendix B.

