6.11 Changes and/or deviations to protocol-planned analyses

In addition to the analyses specified in the CTP a supplementary analysis for the primary endpoint has been added where subjects with potential data issues will be excluded from the main analysis.

The secondary endpoints (average TCS during the AHPS and OPS, average DSS during the AHPS and OPS, average DMS during the AHPS and OPS, and average TCS (EAACI scoring) during BPS and TPS) will be analysed by using the hypothetical estimand and main estimator only.

Local administration site reactions are specified as 'treatment-related local administration site TEAEs.

The reasons for IMP discontinuation will be visualised by a band plot, instead of a Kaplan-Meier plot as the band plot also shows the different reasons for discontinuation.

Physical examination will not be summarized by visit as stated in the CTP, instead a shift table will be made from baseline to end of treatment. 5-, 25-, 75-, and 95 percentiles will not be presented for tabulation of data by visit as stated in the CTP.

The exploratory assessment of the levels of serum antibodies/serum components/serum markers to relevant allergens will not be performed nor reported in a separate document as stated in CTP.

Due to the amount of missing pollen data, it was deemed necessary to perform a visual inspection of all species by pollen station instead of the pollen plots (pollen grains/m³ versus time) as the approach chosen is more precise.

7 Sample size determination

Sample size calculations are based on the primary endpoint, the average TCS during the BPS, which will be square root transformed prior to analysis in order to better approximate the normal distribution. Based on previous ALK SLIT-tablet studies in both adult and paediatric populations, it is assumed that the mean of the square root transformed average TCS during the BPS in the placebo group is 2.5 with corresponding common standard deviation of 1.4 in both placebo and active groups.

Analyses for the primary and secondary estimands will include all randomised subjects and use different multiple imputation strategies to account for missing data. For the purposes of sample size estimation, it is assumed that 5% of observations in the active arm are imputed from the placebo arm. A true relative treatment effect of 25% is assumed, which corresponds to an effective relative treatment effect of 23.75% after placebo imputation.

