Appendix C Examples of SAS code

Table 11: SAS code for primary efficacy analysis

SAS code
proc mixed data= method=reml plots=studentpanel(marginal conditional); class treatment cohort age_group pollen_station; model TCS_sqrt= treatment cohort age_group / ddfm = KenwardRogers residual; random pollen_station (cohort); repeated/group=treatment; lsmeans treatment / cl cov diff; run;

TCS_{sqrt} is the square root of the average TCS.

Table 12: Example for calculating proportion endpoints

SAS code
proc glimmix data =; class treatment cohort age_group pollen_station; model aval / datadays = treatment cohort agegroup / dist=binomial link=logit; random pollen_station(cohort); lsmeans treatment / diff ilink oddsratio cl; run;

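### SAP Appendix B prints σ where the variance σ² belongs in all three back-transformed standard errors; programmed literally, the 95% CI for the absolute difference would be about four times too wide

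*SAP*

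**What the plan says.** SAP section 6.3.2 and Appendix B, Table 10 describe how results for square-root-transformed endpoints return to the original scale. The adjusted means are squared and subtracted. On the standard error, section 6.3.2 says: "For the absolute difference the SE is approximated by using the first order Delta method (first order Taylor approximation". Table 10 names the ingredients. Without multiple imputation, "estimated least square means of the square root transformed endpoint are output along with the associated covariance matrix". With imputation, and after Rubin's rule, "estimated least square means on the square root transformed scale are output along with the associated covariance matrix". The SAS example in Appendix C requests that matrix with "lsmeans treatment / cl cov diff".

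The formulas themselves stand only in Appendix B under Mean and SE. The text there introduces μ and σ² for each arm, together with a covariance, as follows: "be the resulting means and variances for placebo and active treatment and cov be the covariance". The standard errors are then printed as "SE_{Active} = \sqrt{(2\mu_{Active})^2 \sigma_{Active" for active and "SE_{Placebo} = \sqrt{(2\mu_{Placebo})^2 \sigma_{Placebo" for placebo (closing braces cut in both). SE_Difference has σ_Placebo and σ_Active in the same positions and adds the cross-term 2(2μ_Placebo)(-2μ_Active)cov.

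**The concern.** With σ² defined as the variance, σ is the standard error of the adjusted mean on the square-root scale. The delta method for g(μ) = μ² gives Var(μ̂²) ≈ (2μ)² × Var(μ̂) = (2μ)²σ². The printed formulas use (2μ)²σ. This occurs at all four variance terms: one each for active and placebo, and two in the difference. SE_Difference then adds terms on the scale of σ to a covariance on the scale of σ², so its units do not agree.

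The absolute difference is the population summary of both estimands (SAP sections 3.1.1.1 and 3.1.1.2), and its 95% CI is a required output. The same step applies to the primary endpoint, the five key secondary endpoints and the secondary endpoints analysed identically to the primary (SAP section 6.7). It does not apply to the RQLQ and PRQLQ, which are not square-root transformed. The Appendix C code stops at the square-root scale, so someone has to program the back-transformation, and Appendix B is the only formula available to copy. A literal result could place a CI that spans 0 beside a clearly significant p-value.

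**Working it through.** **Inputs.** From SAP section 7 and Table 7: placebo mean 2.5 and SD 1.4 on the square-root scale; FAS with 500 per arm; OC with 450 per arm and a 25% relative effect. For the FAS the true effect is 25%, "which corresponds to an effective relative treatment effect of 23.75% after placebo imputation". Two-sided 5% level. The covariance between adjusted means is not given and is taken as 0 at first.

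**Reproducing the plan's own figure.**
- FAS: active mean = 2.5 × √(1 - 0.2375) = 2.183, so the square-root-scale difference is 0.317. With SD 1.4 and 500 per arm, power is 94.7% (Table 7: 95.0%).
- OC: active mean = 2.5 × √0.75 = 2.165. With 450 per arm, power is 94.8% (Table 7: 94.7%).
- A simulation of the FAS case, drawing 5% of the active arm from placebo, gives 95.3%, 88.6% and 93.3% for the first three criteria (Table 7: 95.0%, 88.3%, 92.8%).

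The inputs are therefore read as the plan intends.

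**Standard error of the difference, FAS.**
- σ² = 1.4²/500 = 0.00392; σ = 0.0626.
- Difference = 2.5² - 2.183² = 6.25 - 4.766 = 1.484.
- Delta method: √(4 × 6.25 × 0.00392 + 4 × 4.766 × 0.00392) = 0.416. CI: 1.484 ± 1.96 × 0.416 = 0.67 to 2.30.
- As printed: √(4 × 6.25 × 0.0626 + 4 × 4.766 × 0.0626) = 1.661. CI: 1.484 ± 1.96 × 1.661 = -1.77 to 4.74.
- Ratio = 1/√σ = 1/√0.0626 = 4.00.
- Square-root-scale test: z = 0.317/√(2 × 0.00392) = 3.58, p about 0.0003.

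**Other cases.**

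| Quantity | Delta method | As printed | Ratio |
|---|---|---|---|
| Placebo adjusted mean, n = 500 | SE 0.313 | SE 1.251 | 4.00 |
| Active adjusted mean, n = 500 | SE 0.273 | SE 1.092 | 4.00 |
| Difference, OC, n = 450 | SE 0.437, CI 0.71 to 2.42 | SE 1.699, CI -1.77 to 4.89 | 3.89 |

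**Effect needed for the printed CI to exclude 0.** With relative effect e and 500 per arm, solve 6.25e = 1.96 × √(4 × 0.0626 × (12.5 - 6.25e)). This gives e = 0.483, that is, about 48%.

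**Sensitivity to the covariance (assumption).** The model has a random pollen-station effect shared by both arms, which makes the covariance positive. The documents give no station variance. Suppose it is a share s of the total variance 1.96, spread over the 65 birch station-by-cohort rows in Appendix D (30 in cohort 1, 35 in cohort 2). Then cov = 1.96s/65 and σ² = 1.96(1 - s)/500 + cov.
- s = 0.05: cov 0.0015, σ² 0.0052; SE of the difference 0.406 against 1.767, ratio 4.4; per-arm ratio 3.7.
- s = 0.30: cov 0.0090, σ² 0.0118; SE of the difference 0.353 against 2.095, ratio 5.9; per-arm ratio 3.0.

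**The case against.** The best defence is that the surrounding text already settles the calculation. The method is named correctly in section 6.3.2 and twice in Table 10, σ² is defined as the variance, and the code outputs variances and a covariance directly. To make the error, a programmer would have to take square roots of the diagonal only and leave the covariance alone. No figure in either document is computed from these formulas, the result would look odd enough to be noticed, and at planning inputs it errs towards a wider interval. A superscript might also have been lost in the rendering of the equations.

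Most of this stands, and it limits the consequence: the harm arises only if the formulas are followed literally. It does not make the formulas right. A lost superscript is unlikely, because the squares on 2μ and on σ in the definition line are intact while all four variance terms lack them; the SAP page itself will settle it.

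Two further cautions are fair. The SAP does not name the scale of the reported p-value. It places the p-value after Rubin's rule and before the back-transformation, which points to the square-root-scale test; a p-value taken from SE_Difference would be affected. And the 65 rows may not match the model's station levels exactly, which would change the sensitivity figures little.

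**Conclusion.** The point holds. The three standard-error formulas contradict the SAP's own definition of σ² and its stated delta method. At the planning inputs with zero covariance, literal use inflates the standard error and the CI width for the absolute difference by 4.0 (FAS) or 3.9 (OC). Under the assumed station shares of 5% to 30%, the factor for the difference is 4.4 to 5.9. The factor depends on sample size and variance.

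The Fieller CI for the relative difference does not use these formulas. On the reading that the test is made on the square-root scale, neither do the p-value and the testing hierarchy. In the planning scenarios the error widens the interval, so it would not create a false positive. This is most likely a notation slip, but it sits in the only written rule for a headline interval and should be corrected.

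**What to change.** Replace σ by σ² at all four variance terms:

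- SE_Active = 2μ_A √(σ²_A)
- SE_Placebo = 2μ_P √(σ²_P)
- SE_Difference = √((2μ_P)²σ²_P + (2μ_A)²σ²_A - 8μ_P μ_A cov)

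Add one sentence stating that σ² and cov are the diagonal and off-diagonal elements of the LS-mean covariance matrix on the square-root scale, Rubin-combined where multiple imputation is used. Then check the analysis program against these formulas.

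The cost is three corrected formulas, one sentence and one program check. The intended method does not change and there is no operational cost.
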